12.4.5 Sensitivity analyses

No sensitivity analyses are planned.

12.4.6 Supplementary analysis

A supplementary clinical question of interest is: how similar is the effect of sabatolimab, as monotherapy and in combination with azacitidine, on prevention of hematologic relapse (i.e., maintenance of CR or CRi) when the AML high risk population is defined based on the biomarker central review? In this supplementary estimand, all except the definition of the population will be the same as the primary estimand (Section 2.1).

The population considered for this supplementary estimand is all adult participants with AML who are in complete remission after having received an aHSCT and at high risk of relapse defined as positive MRD at baseline (determined by central assessment) any time at \geq Day 60 after aHSCT and who have been tapered off immunosuppressive therapy.

12.4.7 Supportive analyses

A supportive clinical question of interest is: how similar is the effect of sabatolimab between the two doses tested (400 mg and 800 mg Q4W) on prevention of hematologic relapse (i.e., maintenance of CR or CRi) in participants with AML at high risk of relapse (MRD positivity)? In this supportive analysis, the proportion of participants with no evidence of hematologic relapse after 6 cycles of treatment with the exact 95% confidence interval will be presented for participants assigned to the sabatolimab dose level tested during the safety run-in part but not selected for the expansion part.

12.5 Analysis supporting secondary objectives

12.5.1 Efficacy and/or Pharmacodynamic endpoint(s)

Relapse-Free Survival (RFS)

RFS is defined as the time from start of treatment to the date of first documented hematologic relapse or death due to any cause, whichever occurs first. RFS will be censored if no RFS event is observed before the first to occur between: (i) the analysis cut-off date, and (ii) the date when a new anti-neoplastic therapy or a donor leucocytes infusion (DLI) is started. The censoring date will be the date of the last adequate response assessment prior to cut-off/start of new anti-neoplastic therapy or DLI. The handling of intercurrent events will be the same as the primary estimand (Section 2.1).

RFS will be analyzed in the FAS population and the RFS distribution will be estimated using the Kaplan-Meier method. Kaplan-Meier curves, medians and 95% confidence intervals of the medians will be presented for each dose cohort.

MRD conversion rate based on central MRD assessment

MRD conversion rate is defined as the proportion of participants with centrally confirmed MRD+ status at baseline converting to MRD- as per central review within the first 6 cycles of study treatment. MRD-negativity will be defined as frequency of LAIP below 0.1%, as determined by a MFC-AML MRD assay by central review. A total of 4 post-baseline bone marrow aspirate or biopsy assessments is planned to be performed during the first 6 cycles of treatment (on Cycle 2 Day 1, Cycle 3 Day 1, Cycle 4 Day 1 and Cycle 7 Day 1). A participant with at least one post-baseline MRD-negative sample as per central review will be considered

Page **118** of **153** Protocol No. CMBG453F12201

as having reached MRD-negativity regardless of the subsequent MRD assessments and regardless of treatment interruption or discontinuation. Only MRD samples collected before start of new anti-neoplastic therapy or DLI will be considered for this analysis.

MRD conversion rate will be analyzed in the FAS population and will be provided with exact 95% confidence interval for each dose cohort.

GvHD-free/relapse-free survival (GRFS)

GRFS is defined as the time from start of treatment to the date of first documented occurrence or worsening of treatment emergent grade III or IV aGvHD or moderate to severe cGvHD requiring initiation of systemic treatment, hematologic relapse, or death due to any cause, whichever occurs first. GRFS will be censored if no GRFS event is observed before the first to occur between: (i) the analysis cut-off date, and (ii) the date when a new anti-neoplastic therapy or a donor leucocytes infusion (DLI) is started. The censoring date will be the date of the last adequate response assessment prior to cut-off/start of new anti-neoplastic therapy or DLI.

GRFS will be analyzed in the FAS population and the GRFS distribution will be estimated using the Kaplan-Meier method. Kaplan-Meier curves, medians and 95% confidence intervals of the medians will be presented for each dose cohort.

12.5.2 Safety endpoints

For all safety analyses, the safety set will be used. All listings and tables will be presented by dose cohort.

Safety summaries (tables, figures) include only data from the on-treatment period with the exception of baseline data which will also be summarized where appropriate (e.g. change from baseline summaries). In addition, a separate summary for death including on treatment and post treatment deaths will be provided. In particular, summary tables for adverse events (AEs) will summarize only on-treatment events, with a start date during the on-treatment period (treatment-emergent AEs).

The overall observation period will be divided into three mutually exclusive segments:

- 1. Pre-treatment period: from day of participant's informed consent to the day before first dose of study treatment
- 2. On-treatment period: from day of first dose of study treatment to 30 days after last dose of study treatment
- 3. Post-treatment period: starting at day 31 after last dose of study treatment.

An overall safety period will be defined from date of first administration of study treatment to 150 days after the last dose of sabatolimab.

Adverse events

Summary tables for adverse events (AEs) will include only AEs that started or worsened during the on-treatment period. The number (and percentage) of participants with treatment emergent adverse events will be summarized by primary system organ class, preferred term and maximum severity.

Separate summaries will be provided for study medication related adverse events, death, serious adverse events, other significant adverse events leading to discontinuation, and adverse events leading to dose adjustment.

Separate summaries will be provided for:

- treatment emergent grade III or grade IV acute GvHD
- treatment emergent moderate to severe chronic GvHD
- treatment-emergent ≥ grade 3 immune-related adverse events not attributed to GvHD

Serious adverse events and non-serious adverse events will be tabulated. All deaths (on-treatment and post-treatment) will be summarized.

In addition, all AEs and SAEs which started during the overall safety period will be summarized. All reported AEs will be listed and those that started during the pre-treatment, overall safety period and post-treatment period will be flagged.

Vital signs

All vital signs abnormalities will be summarized by visit.

Clinical laboratory evaluations

Grading of laboratory values will be assigned programmatically as per National Cancer Institute (NCI) Common Terminology Criteria for Adverse Events (CTCAE) version 5.0. The calculation of CTCAE grades will be based on the observed laboratory values only, clinical assessments will not be taken into account.

CTCAE Grade 0 will be assigned for all non-missing values not graded as 1 or higher.

For laboratory tests where grades are not defined by CTCAE version 5.0, results will be categorized as low/normal/high based on laboratory normal ranges.

For laboratory tests where grades are defined by CTCAE v5.0:

[figure not shown]
- Shift tables using CTCAE v5.0 grades to compare baseline to the worst on-treatment value For laboratory tests where grades are not defined by CTCAE v5.0:
- Shift tables using the low/normal/high/ (low and high) classification to compare baseline to the worst on-treatment value

[figure not shown]

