9.1.1.1 Safety Follow-up

All participants must be followed for safety for 150 days after the last dose of sabatolimab or 30 days after the last dose of azacitidine (Combination cohort) whichever is longer.

After the 30-day on-site safety follow-up visit, participants will be followed via telephone call (or onsite visit if participant happens to be visiting the site) at 90 and 150 days after the last dose of sabatolimab. All safety assessments should be completed as per Table 8-1 and Table 8-2 (Section 10.1.2). However, if the participant begins new anti-neoplastic medication before the end of the safety follow-up period the collection of new SAEs and AEs unrelated to study medication will stop and thereafter only suspected AEs and suspected SAEs will continue to be collected up to the end of the safety follow-up period. Suspected SAEs will continue to be collected beyond the 150-Day safety visit (in Post-Treatment follow-up) see. For female participants of childbearing potential, a pregnancy test will be performed at the time points listed in Table 8-1 and Table 8-2.

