- Dose not changed
- Dose reduced/increased
- Drug interrupted/withdrawn
- 6. its outcome

If the event worsens the event should be reported a second time in the CRF noting the start date when the event worsens in toxicity.

For grade 3 and 4 adverse events only, if improvement to a lower grade is determined a new entry for this event should be reported in the CRF noting the start date when the event improved from having been Grade 3 or Grade 4.

Conditions that were already present at the time of informed consent should be recorded in medical history of the participant.

Adverse event monitoring should be continued for at least

150 days after the last administration of sabatolimab, or 30 days after the last administration of azacitidine, whichever is later.

Page **107** of **153** Protocol No. CMBG453F12201

• Until the start of a new post treatment antineoplastic medication if sooner than the 150 days mentioned above. If a participant starts post treatment antineoplastic medication, then only adverse events suspected to be related to study treatment should be collected, up to 150 days after discontinuation of sabatolimab.

Adverse events (including lab abnormalities that constitute AEs) should be described using a diagnosis whenever possible, rather than individual underlying signs and symptoms. When a clear diagnosis cannot be identified, each sign or symptom should be reported as separate adverse event.

Once an adverse event is detected, it must be followed until its resolution or until it is judged to be permanent (e.g., continuing at the end of the study), and assessment must be made at each visit (or more frequently, if necessary) of any changes in severity, the suspected relationship to the interventions required to treat it, and the outcome.

Disease hematologic relapse / progression (including fatal outcomes), if documented by use of appropriate method [for example, as per ELN 2017 (Döhner et al 2017)], should not be reported as an adverse event. Adverse events separate from the disease hematologic relapse / progression (i.e., deep vein thrombosis at the time of hematologic relapse / progression or hemoptysis concurrent with finding of disease hematologic relapse / progression) will be reported as per usual guidelines used for such events with proper attribution regarding relatedness to the drug.

Information about adverse drug reactions for the investigational drug can be found in the Investigator's Brochure (IB).

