2.7.1 Adverse events (AEs)

Summary tables for adverse events (AEs) will include all AEs that started or worsened during the on-treatment period, including acute Graft-versus-Host Disease (GvHD) and chronic GvHD. When specified, some AEs summaries will include all AEs occurring during the overall safety period.

The number (and percentage) of participants with treatment emergent adverse events will be summarized by primary system organ class (SOC), preferred term (PT) and maximum CTCAE grade. A participant with multiple occurrences of an AE will be counted only once in the respective AE category. A participant with multiple CTCAE grades for the same PT will be summarized under the maximum CTCAE grade recorded for the event. AEs will be assessed according to the Common Terminology Criteria for Adverse Events (CTCAE) version 5.0.

In the AE summaries, the primary SOC will be presented alphabetically, and the PT will be sorted within primary SOC in descending frequency. The sort order for the PT will be based on their frequency in the highest dose level of sabatolimab. The summaries will show 'All grades' (including AEs with missing grade) and 'Grades ≥ 3 '.

The following adverse event summaries will be produced selecting all or a subset of AEs depending on seriousness, relationship to study drugs, and outcome or action taken:

- AEs (by SOC and by PT) and separately those considered related to study drugs
- SAEs
- SAEs with the number of occurrences (an occurrence is defined as > 1 day between start and prior end date of record of same PT)
- Non-SAEs
- SAEs with fatal outcome
- AEs leading to sabatolimab permanent discontinuation

In addition, all AEs and SAE by SOC and PT will be provided on the overall safety period. All reported AEs will be listed and those that started during the pre-treatment, on-treatment and post-treatment period will be flagged.

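### The 150-day summary of all AEs and SAEs covers follow-up in which unrelated events are no longer collected once a new antineoplastic medication starts, so its all-cause incidence is biased downward

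*Protocol*

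**What the plan says.** **Reporting windows.** Protocol 12.5.2 sets two.

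- Main tables: "Summary tables for adverse events (AEs) will include only AEs that started or worsened during the on-treatment period". That period is defined as "On-treatment period: from day of first dose of study treatment to 30 days after last dose of study treatment", and it also defines treatment-emergent events: "with a start date during the on-treatment period (treatment-emergent AEs".
- Overall safety period: first dose to 150 days after the last sabatolimab dose. The protocol adds "In addition, all AEs and SAEs which started during the overall safety period will be summarized". SAP 2.7.1 repeats this: "In addition, all AEs and SAE by SOC and PT will be provided on the overall safety period".

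Neither window ends at new therapy or DLI. SAP 2.1 takes percentages over the participants in the relevant population.

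**Collection.** After a new antineoplastic medication starts, Protocol 9.1.1.1 says "the collection of new SAEs and AEs unrelated to study medication will stop". Section 10.1.1 agrees: "If a participant starts post treatment antineoplastic medication, then only adverse events suspected to be related to study treatment should be collected". Section 10.1.3 has the same restriction for SAEs, although its opening paragraph asks for every SAE, whatever its cause, to the end of safety follow-up.

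**Efficacy, for contrast.** RFS and GRFS follow-up stops at "the date when a new anti-neoplastic therapy or a donor leucocytes infusion (DLI) is started" (Protocol 12.5.1), and MRD conversion uses only samples taken before that point.

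**The concern.** The overall-safety-period summary is presented as all-cause, but part of its follow-up is all-cause and part is suspected-only. A participant who starts new therapy on day 30 after the last dose stays in the denominator for the other 120 days, yet an unrelated event in those days has no route into the numerator.

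The loss is not random. Hematologic relapse ends study treatment (Protocol 6.1.5), so those who relapse are the most likely to go on to new therapy and lose full collection. A cohort with more, or earlier, switching will look safer for events judged unrelated, for a reason that has nothing to do with safety. It is also the only aggregate AE table covering days 31 to 150, so no other table shows the shortfall.

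**Working it through.** The documents give no AE incidence on this point, so there is no planned figure to reproduce. The check compares the windows and then illustrates the size.

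**1. Windows side by side**

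| Time after last dose | Collected, no new therapy | Collected after new antineoplastic medication | Table |
|---|---|---|---|
| Days 1-30 | All AEs/SAEs | Suspected only | Main tables and 150-day summary |
| Days 31-150 | All AEs/SAEs | Suspected only | 150-day summary only |

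The third column applies the suspected-only SAE rule; the opening paragraph of Protocol 10.1.3 conflicts with it.

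**2. Direction.** Events can be missed but not added, and the denominator does not change. The bias in all-cause percentages can only be downward.

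**3. Size in the 150-day summary (illustration).** Assumptions, none from the documents:

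- One unrelated event type with constant hazard h, set to give 20% over 150 days: h = -ln(0.8)/150 = 0.001488 per day. F(t) = 1 - exp(-h·t).
- A share f starts new therapy d days after the last dose, having had 84 days from first to last dose.
- The rest have 12 cycles (11 × 28 = 308 days from first to last dose) or 24 cycles (23 × 28 = 644 days) and no new therapy within 150 days.

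True incidence = f·F(84 + 150) + (1 - f)·F(L + 150), with L = 308 or 644.
Observed incidence = f·F(84 + d) + (1 - f)·F(L + 150).

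With f = 0.60 and d = 30: F(234) = 0.294, F(114) = 0.156, F(458) = 0.494, F(794) = 0.693.

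- L = 308: true 0.6 × 0.294 + 0.4 × 0.494 = 0.374; observed 0.6 × 0.156 + 0.4 × 0.494 = 0.291; relative loss 22%.
- L = 644: true 0.454; observed 0.371; relative loss 18%.

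The same formulas with other inputs (the two figures are for L = 644 and L = 308):

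| f | d | Relative loss |
|---|---|---|
| 0.15 | 30 | 3-5% |
| 0.40 | 30 | 10-13% |
| 0.60 | 14 | 21-25% |
| 0.60 | 60 | 13-16% |
| 0.85 | 30 | 33-36% |

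**4. Main 30-day tables.** If new therapy starts on day 30 or later, nothing is lost. If it starts on day 14, about 8% to 45% of unrelated events in the 30 post-dose days are missed for f from 15% to 85%. That is a loss from the post-dose days only; on-treatment events are still fully collected.

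**The case against.** The strongest reply is that this is one supplementary table in a descriptive safety analysis. No between-cohort safety test is planned. The study ended early and its analyses were cut back. The SAP lists every AE with a period flag, summarises antineoplastic therapy after discontinuation and lists DLIs (2.4.2, 2.7.1), so affected participants can be identified. What is lost is mainly events judged unrelated, often after next-line treatment has begun. All of this stands and limits the consequence. It does not remove the mismatch: the table is still planned and nothing in it warns the reader.

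Several stronger readings are tempting, and the documents do not support them.

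- *All AE tables run to 150 days.* They do not; the main tables stop at 30.
- *GvHD after DLI counts as treatment-emergent throughout.* DLI is prohibited during study treatment (Protocol 6.2.2), and treatment-emergent means onset within 30 days of the last dose. Later onset can enter only the 150-day summary. Whether DLI triggers the collection stop is ambiguous: Protocol 2.1 and 8.2 group it with antineoplastic therapies, while Protocol 12.5.1 and SAP 2.4.2 name it separately.
- *Delayed GvHD and immune-related events are what go missing.* Section 4.1 justifies at least 8 weeks after the first dose, not days 31-150 after the last. Immune-related AEs are by definition associated with study drug (6.5.5.2), so they should remain suspected and be collected. GvHD is assessed at the safety follow-up visits (8.4.4).

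**Conclusion.** The mismatch between collection and reporting is plain in the text, and all-cause incidence in the overall-safety-period summary is biased downward. The size cannot be taken from the documents. At 60% starting new therapy on day 30, the illustration gives 29% observed against 37% true, or 37% against 45%: a relative loss of about 18-22%. It rests on a constant hazard, 84 days from first to last dose for those who switch, and 12 or 24 cycles for the rest.

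A reader might infer that incidence is roughly halved. Counting only the 150 post-dose days, a 20% event would show as 0.6 × (1 - 0.8^(30/150)) + 0.4 × 0.20 = 10.6%. That does not describe this table, which starts at the first dose and includes fully collected on-treatment time. Nor is the loss proportional to relapse. The trigger is new antineoplastic medication, and non-response at Cycle 6 also includes deaths and missing assessments.

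The main 30-day tables share the problem only when new therapy starts within 30 days of the last dose. The effect on GvHD outputs is limited in the abbreviated report: SAP Table 1-1 does not select GvHD incidence and SAP 2.7.1.1 gives listings, though GvHD still enters the general AE tables.

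**What to change.** In Protocol 12.5.2 and SAP 2.7/2.7.1, for the overall-safety-period summary only:

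1. End all-cause AE/SAE counting and time at risk at the earlier of 150 days after the last sabatolimab dose and the day before new antineoplastic therapy.
2. Show suspected events after that date in a separate row.
3. By dose cohort, report the number of participants truncated and events per 100 participant-months. Truncation alone would leave crude percentages too low, so the rate is needed.

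Also:

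4. State whether DLI triggers the collection stop. Flag GvHD with onset after DLI rather than removing it.
5. Reconcile the two SAE rules in Protocol 10.1.3 (every SAE to the end of safety follow-up, against suspected-only after new therapy).

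The cost is wording, one derived end date and a little programming. The dates come from data already planned: antineoplastic therapy since discontinuation (Protocol Tables 8-1 and 8-2) and the DLI listing (SAP 2.4.2). The downside is that late suspected events move to a separate row and must be read alongside the main count.

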12.5.3 Pharmacokinetics

Sabatolimab plasma concentration data will be listed by participant and visit/sampling time point. Descriptive summary statistics will be provided by visit/sampling time point, including mean (arithmetic and geometric), SD, CV (arithmetic and geometric), median, minimum, and maximum, as well as the frequency (n, %) of concentrations below the lower limit of quantification (LLOQ) and reported as zero. Values below the LLOQ will be treated as missing for the calculation of the geometric means and geometric CV%. The minimum observed plasma or serum drug concentration (Cmin or Ctrough) at steady-state will be estimated and reported. Missing values for any PK parameters or concentrations will not be imputed and will be treated

as missing. The concentrations collected on Cycle 3 and later cycles are considered steady-state concentrations for sabatolimab.

All concentration data for sabatolimab versus time profiles will be displayed graphically.

12.7 Interim analyses

Interim analyses are planned for the monitoring of safety data and will be conducted after each dose level cohort of the safety run-in part to determine the recommended dose for expansion (RDE). Decisions will be guided by a Bayesian analysis and the review of all relevant data available from all dose levels evaluated in the ongoing study including safety information, incidence and severity of aGvHD and cGvHD, incidence of DLTs, all CTCAE Grade ≥ 2 toxicity data, PK, and PD data from evaluable participants (Section 6.5.2). Such safety analyses

do not inflate the type I error for the primary efficacy hypothesis testing and thus no adjustment for multiplicity is required.

The primary analysis will be performed after all participants have completed at least 6 cycles of treatment or will be followed for at least 6 months after the first dose of study treatment or will have discontinued from the study earlier. A final analysis will be performed after all participants have completed the study (or discontinued earlier). Formal testing of the primary endpoint with full level alpha will be performed at the primary analysis time point.

